9.3 Recording and Reporting Safety Information

All AEs, SAEs and device deficiencies must be recorded from the time of written informed consent until after the last visit.

All AEs and device deficiencies occurring during the duration of the study must be recorded in patients' medical notes and within the eCRF. The PI is responsible for checking for device deficiencies, A(D)Es and SA(D)Es when participants attend for treatment and follow-up.

- The following events are considered reportable to the MHRA (using the MEDDEV 2.7/3 SAE reporting table) and REC (via the Non-CTIMP safety report to REC form). Any SAE (whether initially considered device related or not)
- Any device deficiency that might have led to a SAE if:
 - Suitable action had not been taken or
 - Intervention had not been made or
 - If circumstances had been less fortunate.
- New findings/updates in relation to already reported events

All reportable events must be first recorded by the investigator using the applicable CTU's SAE/SADE/Device deficiency reporting form and submitted to the Derby CTSU within 24 hours of the research team becoming aware of the event; even if not all information is available at the time (further information should be provided on the CTU's Safety Follow Up Report Form). Any change of condition or other follow-up information should be sent to the CTU as soon as it is available, or at least within 24 hours of the information becoming available. Events will be followed up until the event has been

resolved or a final outcome has been reached. Safety information will be reviewed during trial management group meetings.

Derby CTSU contact information:

Email: [contact].

[contact] or [name] (must be followed up with a written report).

For each reportable event the following information will be collected as a minimum:

- Full details of the event, including a diagnosis
- MedDRA coding (system organ class and preferred term)
- Duration (start and end dates)
- Seriousness criteria
- Outcome.
- Action taken.
- Causality (*i.e.* related to investigational medical device)
- Expectedness

9.3.1 Assessment of AEs and SAEs

9.3.1.1 Severity

The investigator should determine the severity of the AE;

- Mild: no interference with daily activities.
- Moderate: moderate interference with daily activities.
- Severe: considerable interference with daily activities (e.g. inability to work).

NOTE: to avoid confusion or misunderstanding the term "severe" is used to describe the intensity of the event, which may be of relatively minor medical significance, and is NOT the same as "serious" which is described in the safety definitions.

NOTE: changes in severity i.e. from mild to moderate do not constitute a new AE, but changes severity which impact seriousness criteria i.e. from assessed as 'not serious to 'serious', should be reported as a new (serious) event/effect.

9.3.1.2 Causality

Clinical judgement should be used to determine the relationship between use of the investigational medical device (including the medical-surgical procedure) and the occurrence of each AE;

- Not-related: relationship to the device or procedures can be excluded when:
 - The event is not a known side effect of the product category the device belongs to or of similar devices and procedures;
 - The event has no temporal relationship with the use of the investigational device or the procedures;
 - The serious event does not follow a known response pattern to the medical device (if the response pattern is previously known) and is biologically implausible;
 - \circ $\,$ The discontinuation of medical device application or the reduction of the level of

activation/exposure - when clinically feasible - and reintroduction of its use (or increase of the level of activation/exposure), do not impact on the serious event;

- The event involves a body-site or an organ not expected to be affected by the device or procedure;
- The serious event can be attributed to another cause (e.g. an underlying or concurrent illness/ clinical condition, an effect of another device, drug, treatment or other risk factors);
- The event does not depend on a false result given by the investigational device used for diagnosis, when applicable;
- Harms to the subject are not clearly due to use error;
- In order to establish the non-relatedness, not all the criteria listed above might be met at the same time, depending on the type of device/procedures and the serious event.
- Unlikely: the relationship with the use of the device seems not relevant and/or the event can be reasonably explained by another cause, but additional information may be obtained.
- Possible: the relationship with the use of the investigational device is weak but cannot be ruled out completely. Alternative causes are also possible (e.g. an underlying or concurrent illness/ clinical condition or/and an effect of another device, drug or treatment). Cases were relatedness cannot be assessed or no information has been obtained should also be classified as possible.
- Probable: the relationship with the use of the investigational device seems relevant and/or the event cannot reasonably explained by another cause, but additional information may be obtained.
- Causal relationship: the serious event is associated with the investigational device or with procedures beyond reasonable doubt when:
 - The event is a known side effect of the product category the device belongs to or of similar devices and procedures;
 - The event has a temporal relationship with investigational device use/application or procedures;
 - The event involves a body-site or organ that
 - The investigational device or procedures are applied to;
 - The investigational device or procedures have an effect on;
 - The serious event follows a known response pattern to the medical device (if the response pattern is previously known);
 - The discontinuation of medical device application (or reduction of the level of activation/exposure) and reintroduction of its use (or increase of the level of activation/exposure), impact on the serious event (when clinically feasible);
 - Other possible causes (e.g. an underlying or concurrent illness/ clinical condition or/and an effect of another device, drug or treatment) have been adequately ruled out;
 - Harm to the subject is due to error in use;
 - The event depends on a false result given by the investigational device used for diagnosis, when applicable;
 - In order to establish the relatedness, not all the criteria listed above might be met at the same time, depending on the type of device/procedures and the serious event.

Assessment of causality must be made by a medically qualified doctor (usually the principal investigator). If a doctor is unavailable, initial reports should be submitted to the Derby CTSU without the causality assessment, but they must be followed up with a medical assessment as soon as possible.

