8.0 Name and Description of Investigational Device(s)

Isla is a remote surgical wound platform, which runs on all modern phones and tablets. Patients can use Isla to provide data (images and questionnaire responses) in response to pre-programmed text message requests. The new component under investigation is a module for the platform that uses artificial intelligence to identify 'red flags' on submitted wound images which are then prioritised for urgent review by clinicians. Examples of red flags are Discolouration, unexpected fluids/tissue, sutures/clips observed, incision

In this study, Isla will be offered to all adult patients (18 or over) having coronary artery bypass graft (CABG) surgery at the participating sites.. Isla is intended to capture information on surgical wounds remotely. The new AI module prioritises images with a concern for urgent review by a clinician. We plan to recruit 120 patients of which 60 will receive monitoring through Isla.

Isla is a digital platform. Isla sends patients text message requests for data about their wound. Patients can use their smart phone or ipad to take a photo of their wound which they send using their smart phone or email. They also provide responses to the modified UKHSA post discharge wound monitoring questionnaire.

Data is transferred securely using state-of-the art SHA256 encryption in transit and at rest. Standards include conformity with medical device regulations, General Data Protection Regulation (GDPR), NHS Digital Technologies Assessment Criteria (DTAC), the STARD-AI initiative and NICE Evidence Standards Framework for Digital Health.

Patients only use their own mobile or computing devices. There is no App to download. There is no physical contact with the Isla device. The Isla product is purely software.

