9.0 PHARMACOVIGILANCE

9.1 Definitions

Term	Definition						
Adverse Event (AE)	Any untoward medical occurrence, unintended disease or injury, or						
	untoward clinical signs (including abnormal laboratory findings) in						
	subjects, users or other persons, where or not related to the						
	investigational medical device and whether anticipated or						
	unanticipated.						
Adverse Device	An adverse event related to the use of an investigational medical						
Effect (ADE)	device.						
	 NOTE: this definition includes: AEs resulting from insufficient or inadequate instructions for use, deployment, implantation, installation, or operation, or any malfunction of the investigational medical device. Any event resulting from use error or from intentional misuse of the investigational medical device. 						
	Comparator' if the comparator is a medical device.						
Serious Adverse Event (SAE)	 An adverse event that led to any of the following: death serious deterioration in the health of the subject, users, or other persons as defined by one of more of the following a life-threatening illness or injury, or a permanent impairment of a body structure or a body function including chronic diseases, or in-patient of prolonged hospitalisation, or 						

	 medical or surgical intervention to prevent life-threatening
	illness or injury, or permanent impairment to a body structure
	of a body function,
	 foetal distress, foetal death, a congenital abnormality, or birth defect
	including physical or mental impairment.
	NOTE: Planned hospitalisation for a pre-existing condition, or a
	procedure required by the CIP without a serious deterioration in health,
	is not considered a SAE.
Serious Adverse	An adverse device effect that has resulted in any of the consequences
Device Effect (SADE)	characteristic of a serious adverse event.
Unanticipated	A serious adverse device effect which by its nature, incidence, severity or
Serious Adverse	outcome has not been identified in the current risk assessment.
Device Effect	
(USADE)	NOTE: Anticipated serious adverse device effect (ASADE) is an effect which by
(,	its nature, incidence, severity or outcome has been identified in the risk
	assessment.
Device Deficiency	Inadequacy of a medical device with respect to its identity, quality, durability,
,	reliability, usability, safety or performance.
	NOTE: This definition includes:
	• Malfunctions, use errors, and inadequacy in the information supplies

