11.8 Other Statistical Considerations

A health economic analysis plan and early model have been prepared and have informed the design of this study particularly with respect to data collection. See next section for details of the economic evaluation.

Adverse device effects and adverse events , will be reported using frequencies and percentages.

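### The causality rule in 9.3.1.2 takes in an undefined surgical procedure, so a CABG-caused wound infection can be graded as related to a software device

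*Protocol*

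**What the plan says.** The causality instruction in Protocol 9.3.1.2 is to use clinical judgement on the "relationship between use of the investigational medical device (including the medical-surgical procedure) and the occurrence of each AE". Two of the five grades then extend beyond the device. Not-related applies where the "relationship to the device or procedures can be excluded when" a list of conditions holds. Causal relationship applies where "the serious event is associated with the investigational device or with procedures beyond reasonable doubt when" a second list holds. Among the items in that second list are "The event is a known side effect of the product category the device belongs to or of similar devices and procedures" and "The event has a temporal relationship with investigational device use/application or procedures". Unlikely, Possible and Probable are worded for the device alone.

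Elsewhere the protocol keeps to the device. Section 9.1 defines an ADE as "An adverse event related to the use of an investigational medical" device. The minimum data set for a reportable event in 9.3 has one causality item, which asks about the device. Section 9.3.1.3 requires an expectedness assessment only for events judged related to device use. Section 8.0 says of the product: "There is no physical contact with the Isla device. The Isla product is purely software".

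On analysis, 11.8 states: "Adverse device effects and adverse events , will be reported using frequencies and percentages". Section 11.6 tabulates them by treatment received.

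**The concern.** Wording that joins a device to its procedure suits a product that is implanted or applied by an operation. Isla is neither. The one medical-surgical procedure common to all participants is the CABG, which both arms have before randomisation (section 4). If the assessor takes the bracketed words to mean the CABG, relatedness becomes a link to the software or a link to the operation, and an ordinary post-operative wound infection can qualify through the second route.

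Relatedness decides whether an event becomes an ADE, a SADE or, after the expectedness step, a USADE. On the wide reading the ADE table would partly or wholly repeat the background infection rate and would say little about the software. The table would also sit badly with 9.2, which expects no device-caused events affecting patients. Grading is done by a doctor, usually the principal investigator, at each of two sites, so the count could also depend on how each site reads one phrase.

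**Working it through.** **Inputs**
- 60 patients receive Isla (8.0).
- Wound infection rate 8% (9.2 and 11.1).
- No device-caused events affecting patients are expected (9.2).

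**Step 1: reproduce the plan's own figures.** The Trial Summary expects around 12 patients per group with a wound problem and 4 to 5 with an infection. From the rates in 11.1, 60 × 0.21 = 12.6 and 60 × 0.08 = 4.8. Both agree.

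**Step 2: set the texts side by side.**

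| Place | What the event is related to |
|---|---|
| 9.1, ADE definition | device use |
| 9.3, recorded causality item | device |
| 9.3.1.2, opening instruction | device use, with the medical-surgical procedure included |
| 9.3.1.2, Not-related and Causal relationship | device or procedures |
| 9.3.1.2, Unlikely, Possible, Probable | device |
| 9.3.1.3, expectedness step | device use |

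The scale therefore asks one question at its two ends and a narrower one in the middle.

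**Step 3: grade a test event.** Take a sternal wound infection in an Isla patient, with no missed, false or late flag.
- *Items pointing to Causal relationship:* it follows a procedure in time; it is at the body site to which the procedure was applied; and it is a known side effect, if similar procedures include CABG.
- *Causal items it does not meet:* a known response pattern to the device, and dependence on a false device result.
- *Items pointing to Not-related:* it does not depend on a false result; and it has another cause, if the CABG counts as something other than the device side of the question.

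Both lists end by saying that not every item need hold at once. The same infection can thus support opposite grades, and which one is chosen turns on the undefined word.

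**Step 4: bound the ADE count in the 60 Isla patients, with no true device effect.**
- *Device-only reading:* about 0 of 60. If 0 is observed, the exact 95% upper limit is 1 − 0.025^(1/60) = 6.0%.
- *Wide reading, every infection graded related:* expected 60 × 0.08 = 4.8, or 8%. The 95% binomial range is 1 to 9. The chance of at least one is 1 − 0.92^60 = 0.993.

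**The case against.** The strongest defence is that the rule calls for clinical judgement and contains its own safeguards. Attribution to another cause, and no dependence on a false result, both support Not-related. The causal list includes other causes having been ruled out. Three of the five grades ask about the device only. Section 9.2 lists infection and its consequences as expected events after surgery. The bracketed words could also be read as empty, since Isla has no procedure, and 7.6 uses the word procedures for study activities such as image requests, surveys and calls.

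Much of this stands. A reader might infer that every post-CABG infection is automatically device-related, and the text does not support that: an assessor could properly choose Not-related or Unlikely. A reader might also infer that control patients will fill the ADE table. The 9.1 definition requires use of the device, and so would keep them out. Nor does the text support the view that a true device signal would be lost, because 9.2 requires missed and false flags to be recorded separately as device deficiencies. Extending the count to all wound problems (15% to 21%) is not supported either: the Trial Summary includes discolouration and observed sutures or clips among these, while the causal grade is worded for serious events.

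What the defence does not do is settle the question put to the assessor. The usage in 7.6 might explain the bare word procedures, but it cannot explain medical-surgical. The other-cause item helps only once it is decided that the CABG is a cause separate from the device, and the opening instruction blurs exactly that.

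**Conclusion.** The inconsistency is real and stands in the text: 9.3.1.2 adds an undefined procedure to a causality question that 9.1, 9.3, 9.3.1.3 and the middle grades confine to the device. It permits surgical wound infections to be graded as related, and permits the two sites to differ.

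The intervention-arm ADE count could range from about 0 to about 5 of 60 with no device effect. The upper end assumes that all infections occur at 8%, that each is graded related through the operation, and that this grade counts as an ADE; the protocol does not say which grades count. It is a bound, not a forecast.

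The consequence is limited to ADE, SADE and USADE classification and the descriptive ADE table. Under 9.3 any SAE is reportable whether or not it is device-related, so that trigger is untouched. ADE counts are neither a primary outcome (3.0) nor a progression criterion (11.2.2). The change is worth making because it costs little and corrects a rule that is stated, not merely left open.

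**What to change.** In 9.3.1.2, delete the bracketed words on the medical-surgical procedure. Define procedures there as investigation-specific steps: image request and submission, AI flagging, and image review. State that the index CABG and any re-operation are not among them. Then align 9.1, 9.3, 9.3.1.2 and 9.3.1.3 so that all ask the same device-only question.

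Alternatively, record relatedness to the device and relatedness to the operation as two separate items, and count only the first towards ADEs.

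Either is a change of wording or form guidance with a short note to sites. No extra patients are needed. The small cost is that events already graded should be re-checked against the clarified wording.

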9.3.1.3 Expectedness

The assessment of expectedness is only required if the event is deemed to be related to use of the investigational medical device.

- **Anticipated:** The medical device is thought to have a causal relationship with the event and the event is listed within the reference information used to assign causality
- **Unanticipated:** The medical device is thought to have a causal relationship with the event and the event is NOT listed within the reference information.
- Unanticipated, causal relationship and seriousness = USADE
- •

The expectedness assessment is delegated to Chief Investigator.

CIP will be used for expectedness assessments.

9.3.2 Expedited safety reporting

For trials of investigational medical devices that are non CE-marked all reportable events must be reported to the MHRA using the MEDDEV 2.7/3 SAE reporting table (or MDCG 2020-10/2 SAE reporting table) via the MORE portal and the manufacturer. All events which indicate an imminent risk of death, serious injury, or serious illness that requires prompt remedial action for patients, users or other persons should be reported to the MHRA within 2 calendar days of Sponsor awareness. Any other reportable events must be reported within 7 calendar days of awareness by the Sponsor. In addition, all USADEs must be reported to the REC.

In addition to the reporting of individual serious adverse events as detailed above, quarterly summary reports of all serious adverse events will also be provided (Items I, II & III in tabular format) and should include the following:

- I. number of serious adverse events
- II. number of participants affected by those events
- III. percentage of the total number of enrolled participants affected by those events
- IV. A summary analysis of the serious events together with the manufacturer's conclusions

The first quarterly report should be submitted the first quarter after the first patient has been treated. The SAE reporting form should be submitted via https://more.mhra.gov.uk/login. All reporting to MHRA will be coordinated by Derby Clinical Trials Unit with assistance from ISLA.

9.4 Pregnancy reporting

It is unlikely, but possible, that pregnant women will be undergoing coronary artery bypass graft surgery. Due to the non-invasive nature of the study – taking a digital photo of a surgical wound and answering questions about a surgical wound, it is not deemed necessary to notify the CTU of pregnant

participants or follow them up until the outcome of the pregnancy. As per standard reporting criteria, if at any stage an event occurs that meets the criterion for an SAE then it must be reported as such.

9.5 Reporting Urgent Safety Measures

If any urgent safety measure is taken the research team should inform the Derby CTSU within 24 hours using the Derby CTSU's safety incident reporting form. The Derby CTSU will inform the MHRA, REC and participating sites of the measures taken and the circumstances giving rise to those measures within 3 days on implementation of the urgent safety measure.

10.0 DATA HANDLING

Study data will be entered at site into electronic case report forms (eCRF) directly by study personnel. The study will use an electronic data capture (EDC) system to store all data securely. The database will be a cloud-based EDC, built by Derby CTSU and hosted by a fully validated 3rd party vendor. Derby CTSU will be responsible for database design, build and data validation while the provider of the EDC will be responsible for hosting and storage of the study data. Access to the EDC will be via a unique username and password, and permissions for data entry and management assigned based on study roles.

After data entry is performed, validation checks will be applied to the data to ensure accuracy and consistency according to the data validation plan. All data queries generated as a result of these checks will be available online for resolution by the sites. Processing of study data and monitoring for consistency, validity and quality will be undertaken by study statisticians, data and trial manager on an ongoing basis during recruitment. After data entry is complete and all data queries have been resolved, the database will be locked and released for statistical analysis.

Participants will be identified by their unique Participant ID number assigned by the EDC system which will be manually added to each participant's Isla record. The link between participant ID and NHS number and Isla unique URL link – or other means of re-identification, will be stored securely locally at each hospital with restricted access.

Participant reported outcomes will be captured via a series of participant questionnaires (outlined in Section 3.2). The link for the on-line survey, hosted on Dacima, will be sent to patients via text or email. Paper copies will be available if requested and will be posted to the participants. Participants will complete their responses within the questionnaire booklet, and return the completed document to site, for entry onto the trial database.

